#### 5.8.3. ECG EVALUATIONS

12-lead ECG assessments will be recorded only at screening. However, if clinically applicable, additional ECG findings will be collected during treatment period. When applicable, descriptive statistics for change from baseline to post-baseline for the following ECG data will be presented: heart rate (HR), PR interval, QRS duration, QT interval, and QTc interval.

The interpretation of ECG results will also be presented, where 'NA' (not applicable) will be counted as no record of abnormalities, i.e., normal.

For this study, no summary statistics for ECG data will be presented. ECG data will only be presented in listing.

#### 5.8.4. VITAL SIGNS PARAMETERS

Vital sign will be measured at the time points specified in Schedule 1 and Schedule 3 of the protocol. Additional vital signs measurements may be performed during the study if clinically indicated. On dosing days, vital signs should be obtained ≤30 minutes before the start of the infusion, ≤15 minutes after completion of the infusion, and between 30 minutes and 1 hour after completion of the infusion.

Summary statistics for vital signs measured at each treatment visit, and the change from post-infusion to pre-infusion at each visit, will also be presented.

Number of subjects with PCI vital signs data will also be presented. Potentially clinically important vital signs values are defined as follow:

Variable	Potentially Clinically Important Criteria
Systolic Blood Pressure	< 90 mmHg;
	≥ 140 mmHg.
Diastolic Blood Pressure	< 60 mmHg;
	≥ 90 mmHg.
Pulse	≤ 50 bpm;
	≥ 100 bpm.

Height and weight, obtained at the screening visit, will be summarized within the demographics table.

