7.4 Safety Analyses

The following will be assessed:

- Adverse events (including treatment-emergent adverse events).
- Summary statistics and changes from baseline to post-baseline for laboratory testing, vital signs, and, if applicable, any ECG findings will be presented.
- Results of C1 INH antibody testing will be reported for individual subjects and summarized as appropriate.

NOTE: Treatment-emergent events include all adverse events that start during the treatment period (and up to 7 days after the last dose of investigational product) and were not seen at baseline, or were seen at baseline but worsened in frequency and/or severity during the treatment period (and up to 7 days after the last dose of investigational product).

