#### 4.3. SAFETY ASSESSMENTS

The following will be assessed:

- Adverse events (including treatment-emergent adverse events).
- Summary statistics and changes from baseline to post-baseline for laboratory testing, vital signs, and, if applicable, any electrocardiogram (ECG) findings will be presented.
- Results of C1-INH antibody testing will be reported for individual subjects and summarized as appropriate.

\\SW20RND01\VistaTempDir\Temp28232\Shire\_0624\_209\_SAP\_v1 0.docx Document:

Template No: CS\_TP\_BS016 Revision 4 Reference: CS\_WI\_BS005

Version Number:

Version Date:

1.0

21Jul2017

Effective Date: 01Apr2016

Author:

Shire
PROTOCOL: 0624-209
Page 12 of 35

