#### 5.8.2. **CLINICAL LABORATORY EVALUATION**

Laboratory values will be obtained for hematology, clinical chemistry, coagulation, virology and urinalysis at the time points specified in Schedule 1 and Schedule 3 of the protocol. The laboratory tests will be performed by a central laboratory.

Descriptive statistics will be provided hematology, clinical chemistry and coagulation data at time points specified in Schedule 1 and Schedule 3 of the protocol. Descriptive statistics for change from baseline to post-baseline, and shifts with respect to normal ranges for the same period will also be presented. Data listings will be provided for all subjects. Laboratory values outside the normal range will be flagged.

Baseline is denoted as Visit 1.

Number of subjects with potentially clinically important (PCI) lab values will also be presented. Potentially clinically important lab values are defined as per Table 1 below.

\\SW20RND01\VistaTempDir\Temp28232\Shire\_0624\_209\_SAP\_v1 0.docx Document: Version Number: Author:

Reference: CS\_WI\_BS005

Version Date:

Template No: CS\_TP\_BS016 Revision 4

1.0

Table 1: Potentially important lab values

Test Item	Unit	Reference range	Criterion *1
WDC (11 B)	/micro L	2222 2222	> 15000
WBC (blood)		3300 - 9000	< 2000
Eosinophils (rel)	%	0.0 - 8.0	> 10.0
N	/micro L	(NT/A)	> 11000
Neutrophils (abs)		(N/A)	< 1000
Lymphocytes (abs)	/micro L	(N/A)	> 20000
Lymphocytes (abs)		(IV/A)	< 500
	g/dL	M: 13.5 - 17.5	>(BL) + 4.0
hemoglobin (blood)		F: 11.5 - 15.0	· (DL) · 4.0
		11110 1510	<(BL) – 3.0
platelet count	x10^4	14.0 - 34.0	> 60.0
	/micro L		< 10.0
aPTT-second	sec	25.0 - 36.0	> 90.0
PT-INR	(N/A)	0.85 - 1.15	> 2.875
BUN	mg/dL	8 - 23	> (BL) x 2.0
creatinine	mg/dL	M: 0.61 - 1.04 F: 0.47 - 0.79	> (BL) x 2.0
1 ( )	mg/dL	70 100	> 250
glucose (serum)		70 - 109	< 40
1.	mEq/L	127 147	> 155
sodium		137 - 147	< 130
	mEq/L	25.50	> 6.0
potassium		3.5 - 5.0	< 3.0
AST	U/L	10 - 40	> 200
ALT	U/L	5 – 45	> 225
ALP	U/L	100 - 325	> 1625
CPK	U/L	M: 60 - 270	M: > 1350
CPK		F: 40 - 150	F: > 750
total bilirubin	mg/dL	0.2 - 1.2	> 3.6
calcium	mg/dL	8.4 - 10.4	> 12.5
calcium		8.4 - 10.4	< 7.0
phosphorus	mg/dL	2.5 - 4.5	< 2.0

\*1 BL (Baseline) is Visit 1. When the sample is not collected at Visit 1, the alarm for variation (ratio/difference) is not performed.

\\SW20RND01\\VistaTempDir\Temp28232\\Shire\_0624\_209\_SAP\_v1 0.docx Version Number: Document: Author:

Version Date: 21Jul2017 Reference: CS\_WI\_BS005

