Table 14.3.1.3.2 Serious Treatment-emergent Adverse Events by Preferred Term (Intent-to-Treat Safety Analysis Set

Table 14.3.2.1 Treatment-emergent Adverse Events by Maximum Severity, System Organ Class and Preferred Term (Intent-to-Treat Safety Analysis Set)

Table 14.3.2.2 Treatment-emergent Adverse Events Considered Related to Investigational Product by System Organ Class and Preferred Term (Intent-to-Treat Safety Analysis Set)

Table 14.3.4.1 Quantitative Clinical Laboratory Results: Hematology (Intent-to-Treat Safety Analysis Set)

Table 14.3.4.2 Quantitative Clinical Laboratory Results: Clinical Chemistry (Intent-to-Treat Safety Analysis Set)

Table 14.3.4.3 Quantitative Clinical Laboratory Results: Coagulation (Intent-to-Treat Safety Analysis Set)

Table 14.3.4.4 Quantitative Clinical Laboratory Results: Urinalysis (Intent-to-Treat Safety Analysis Set)

Table 14.3.4.5 Shift from Baseline in Clinical Laboratory Results: Hematology (Intent-to-Treat Safety Analysis Set)

Table 14.3.4.6 Shift from Baseline in Clinical Laboratory Results: Clinical Chemistry (Intent-to-Treat Safety Analysis Set)

Table 14.3.4.7 Shift from Baseline in Clinical Laboratory Results: Coagulation (Intent-to-Treat Safety Analysis Set)

Table 14.3.4.8 Shift from Baseline in Clinical Laboratory Results: Urinalysis (Intent-to-Treat Safety Analysis Set)

Table 14.3.4.9 Subjects with Potentially Clinically Important (PCI) Laboratory Results (Intent-to-Treat Safety Analysis Set)

Table 14.3.5.1 Actual Values and Change from Baseline in Vital Signs (Intent-to-Treat Safety Analysis Set)

Table 14.3.5.2 Potentially Clinically Important Vital Signs Results (Intent-to-Treat Safety Analysis Set)

Table 14.3.6 Study Drug Exposure (Intent-to-Treat Safety Analysis Set)

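### SAP 5.8.4 words the within-visit vital-sign change in reverse, and does not carry through the change from baseline planned elsewhere

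*SAP*

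**What the plan says.** SAP Section 5.8.4 names two summaries of vital-sign measurements. The first is "Summary statistics for vital signs measured at each treatment visit". The second is "the change from post-infusion to pre-infusion at each visit". It also plans counts of subjects beyond fixed limits for systolic pressure, diastolic pressure and pulse. On dosing days there is one reading before the infusion and two after it: "≤15 minutes after completion of the infusion, and between 30 minutes and 1 hour after completion of the infusion".

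Other places plan a change from baseline for the same data:

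- Protocol 7.4: "Summary statistics and changes from baseline to post-baseline for laboratory testing, vital signs, and, if applicable, any ECG findings will be presented".
- SAP 4.3 repeats the commitment: "Summary statistics and changes from baseline to post-baseline for laboratory testing, vital signs".
- SAP 9.1.1 lists "Table 14.3.5.1 Actual Values and Change from Baseline in Vital Signs".

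For laboratory data, SAP 5.8.2 states "Baseline is denoted as Visit 1". Section 5.8.4 has no equivalent statement. SAP 6.2, which records departures from the protocol's analyses, names only the analysis of clinical relief.

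**The concern.** There are two linked problems in the section that a programmer would work from.

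The first is direction. A change from A to B is B minus A. With post-infusion as A and pre-infusion as B, the result is pre minus post. A fall in blood pressure after the infusion would appear as a positive change, and a rise in pulse as a negative one.

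The second is that 5.8.4 does not agree with the rest of the plan. A table titled as change from baseline cannot be built from 5.8.4, because that section neither mentions such a change nor says what the baseline is.

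Safety and tolerability form the first objective listed for the study, and the drug is given by repeated infusion. The change column is where a reader would look for a typical shift in blood pressure or pulse around the infusion, so its sign and reference point should be beyond doubt.

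**Working it through.** The plan gives no figure to reproduce here. The check is a comparison of texts and one line of arithmetic.

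**1. Direction by the SAP's own usage.** Sections 4.3, 5.8.2 and 5.8.3 all describe change as running from baseline to post-baseline, that is, from the earlier value to the later one. Applying the same grammar to 5.8.4:

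- as written: change = pre-infusion − post-infusion
- conventional: change = post-infusion − pre-infusion

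**2. Effect on the sign.** Assume, for illustration, systolic pressure of 120 mmHg before and 100 mmHg after the infusion.

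- as written: 120 − 100 = +20
- conventional: 100 − 120 = −20

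The size is the same and the sign is opposite. Of the descriptive statistics in SAP 5.1, the mean and median change sign, the minimum and maximum change sign and swap places, and the standard deviation and n stay the same.

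**3. How many visits are touched.** Protocol Schedule 1 places vital signs at Dosing Visits 1 and 2 and then at every even visit from 4 to 24: 2 + 11 = 13 visits. Subjects who independently self-administer at home have no readings at Visits 10, 12, 14, 18, 20 and 22, which leaves 13 − 6 = 7. The within-visit change therefore applies to three variables at between 7 and 13 visits per subject completing treatment.

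**4. Change from baseline.**

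| Place | Change from baseline planned? | Baseline stated for vital signs? |
|---|---|---|
| Protocol 7.4 | Yes | No |
| SAP 4.3 | Yes | No |
| SAP 5.8.4 | Not mentioned | No |
| SAP 9.1.1, title of Table 14.3.5.1 | Yes | No |
| SAP 6.2 | No departure declared | Not applicable |

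**5. What is left open.** Vital signs are taken at Screening and at Dosing Visit 1, with three readings on a dosing day. Several values could serve as baseline, and 5.8.4 does not choose among them. Nor does it say whether the first post-infusion reading, the second, or both enter the within-visit change.

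**6. A visit that a within-visit change cannot cover.** Schedule 3 requires vital signs at the Early Discontinuation Visit but schedules no infusion there. Only a change from a study baseline can be computed at that visit.

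**The case against.** The best reply is that this is loose English. The phrase may mean the post-infusion value relative to the pre-infusion value, and 5.8.4 gives no formula that fixes pre minus post. That is plausible, and a careful programmer may well do the conventional thing. It makes the consequence conditional: the sign is reversed if the text is followed literally. It does not make the text right, because the literal reading is also the one that matches the SAP's usage elsewhere.

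A second reply is that the pre-infusion value is each visit's own baseline, so the table title fits. Section 5.8.4 does not say this, it would not be the protocol's change from baseline to post-baseline, and it gives nothing at the Early Discontinuation Visit.

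A reader might go further and infer that the SAP has dropped change from baseline altogether, that drift over the 12 weeks would be invisible, or that infusion-related hypotension or tachycardia would be hidden. The documents do not support any of these:

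- SAP 4.3 and the title of Table 14.3.5.1 still plan the change from baseline.
- Summaries of actual values at each treatment visit would show drift in the group.
- The potentially clinically important limits are absolute (for example systolic below 90 mmHg, pulse at or above 100 bpm), so the counts in Table 14.3.5.2 do not depend on the sign of a change. An assumed fall from 120 to 85 mmHg would still be counted.
- Listings 16.2.8.2.1 and 16.2.8.2.2 cover vital signs by subject, and Protocol 9.1.5 has the investigator judge whether a vital-sign change is an adverse event.

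These safeguards do not replace the change summary. An assumed systolic fall from 135 to 100 mmHg crosses neither limit (below 90, or 140 and above), so in the tables the paired change is what captures it.

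**Conclusion.** The point holds as a drafting error with limited reach. Followed literally, SAP 5.8.4 reverses the sign of the within-visit change for systolic pressure, diastolic pressure and pulse. The section is also inconsistent with SAP 4.3, with the title of Table 14.3.5.1 and with Protocol 7.4, because it does not carry through the change from baseline or define one for vital signs. This is an inconsistency inside the SAP and with the protocol; the SAP as a whole still plans the analysis.

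The effect is confined to derived change summaries, which would be mis-signed or left without a defined reference. The analysis is descriptive and the study needs a minimum of 6 completers, so individual values can be read directly. The blood pressure values used above are illustrations and do not come from the documents. The sign conclusion assumes that the sentence is programmed as written. Priority is low, but the correction is worth making because it is simple.

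**What to change.** Revise SAP 5.8.4 as follows:

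1. Define within-visit change as post-infusion minus pre-infusion, computed separately for each of the two post-infusion times.
2. Define the vital-sign baseline. The pre-infusion value at Dosing Visit 1 is a natural choice: it is in line with the Visit 1 baseline used for laboratory data, and Protocol Section 6 keeps the vital signs relative to dosing when Screening and Dosing Visit 1 fall on one day. The documents do not compel this choice, so the SAP should state whichever is adopted.
3. Add change from that baseline at post-baseline visits, including the Early Discontinuation Visit, and say which reading on a dosing day is used.
4. Show both changes, labelled, in Table 14.3.5.1, so that 5.8.4 agrees with SAP 4.3 and Protocol 7.4.

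The cost is a few sentences of SAP text and the matching table shell. The readings needed are already scheduled, so no new data are required. If the table has already been programmed, check the sign of the derivation against the revised text.

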#### 5.8.5. PHYSICAL EXAMINATION

No summary statistics will be presented for physical examination.

[figure not shown]
\\SW20RND01\VistaTempDir\Temp28232\Shire 0624 209 SAP v1 0.docx Document:

Author: Version Number: 1.0 Version Date: 21Jul2017

Template No: CS TP BS016 Revision 4 Reference: CS\_WI\_BS005

Effective Date: 01Apr2016

Copyright © 2009, 2010, 2012, 2016 Quintiles Transnational Corp. All rights reserved. The contents of this document are confidential and proprietary to Quintiles Transnational Corp. Unauthorized use, disclosure or reproduction is strictly prohibited.

As per guidance in Completion Guidelines, any baseline abnormal physical examinations will be recorded in the Medical History Form. Any post Dosing Visit 1 clinically significant physical examination findings or worsening of previous conditions will be recorded in the Adverse Event form."

#### 5.8.6. MEDICAL HISTORY

Medical history will be coded according to MedDRA version 19.0 central coding dictionary. Medical history will be presented by SOC and PT, and will be sorted by SOC in alphabetical order, then within SOC, PT will be sorted in descending frequency.

#### 5.8.7. PRIOR AND CONCOMITANT MEDICATION

Prior medications are any medications received for the management of HAE within 12 months before Day 1 and all other medications taken within 1 week before Dosing Visit 1.

Concomitant medications are any medications taken from the start of Dosing Visit 1 through the 1-Month Post-treatment Follow-up Visit.

Prior and concomitant medications will be coded according to World Health Organization (WHO) drug dictionary version 01JUN2016. Summary of medications will be divided into medications given for HAE long-term prevention, HAE short-term prevention, HAE acute treatment which included either C1 Inhibitor or Tranexamic Acid, HAE symptom management which indication included acute treatment and medication is not C1 Inhibitor or Tranexamic Acid, and all other medications used. This will be presented by ATC Level 1 and PT. Preferred Term is defined as basename from WHO drug dictionary. Table will be sorted by indications and ATC Level 1 in alphabetical order, then within ATC Level 1, PT will be sorted in descending frequency. Details of prior and concomitant medications used will be provided in one listing.

#### 5.8.8. TREATMENT COMPLIANCE

Treatment compliance is defined by 24 complete infusions, and no dose interruption. Dose interruption means that the gap between any two consecutive doses is at least 6 days.

The compliance for subjects who have no dose interruption or subjects whose treatment duration is less than 12 weeks (84 days) is calculated as:

$$(\%) = \frac{(}{}$$
 x100

The compliance for subjects who have dose interruption and the treatment duration is greater than 12 weeks (84 days) is calculated as:

where 3.5 is the average number of days between 2 infusions in one week.

Document: \\SW20RND01\\VistaTempDir\Temp28232\\Shire\_0624\_209\_SAP\_v1 0.docx

Author: PPD Version Number: 1.0
Version Date: 21Jul2017

Template No: CS TP BS016 Revision 4 Reference: CS WI BS005

PROTOCOL: 0624-209 Page 25 of 35

1.0

Reference: CS\_WI\_BS005

# 5.9. IMMUNOGENICITY (C1-INH ANTIBODY) AND PHARMACOKINETIC CONCENTRATIONS AND PHARMACODYNAMICS LEVELS

The concentrations of C1-INH antigen (protein volume), functional C1-INH activity (potency), and complement C4 and C1q for individual subjects will be determined using fully validated bioanalytical methods, and will be listed and summarized using descriptive statistics at each time point. C1q concentrations will be assessed at baseline only (ie, pre-infusion, Dosing Visit 1).

The Antibody results will be listed and summarized using descriptive statistics at each nominal time point.

\\SW20RND01\VistaTempDir\Temp28232\Shire 0624 209 SAP v1 0.docx Document: PPD Version Number: Author:

Version Date: 21Jul2017

Template No: CS\_TP\_BS016 Revision 4

PROTOCOL: 0624-209 Page 26 of 35

1.0

21Jul2017

